4.2. Secondary Endpoints

- Area under the curve (AUC) of mepolizumab and reslizumab from time zero to infinity (AUC_{0-inf})
- Maximum concentration (C_{max}) of mepolizumab and reslizumab
- Model parameter estimates for mepolizumab and reslizumab exposure-response models (exposure parameter versus AUEC_{0-t} or ΔEosinophil_{dec, max})

4.3. Exploratory Endpoints

- Additional pharmacokinetic parameters for mepolizumab and reslizumab, including time of maximum concentration (T_{max}), elimination rate constant (K_{el}), area under the curve from time 0 to end of study (AUC_{0-t}), half-life (t_{1/2}), apparent clearance (CL/F), and apparent volume of distribution (V/F).
- Time course profiles, maximum increase/decrease from baseline, and AUEC for plasma proteomics and small RNA transcriptomics (set of markers be determined)

5. Analysis Populations

- For all analyses, subjects will be analyzed according to the dose and treatment received, not the dose and treatment to which subjects were randomized.
- The PD population will include all subjects who receive study drug and have at least 1 estimable PD parameter after dosing. For baseline-adjusted analyses, subjects must also have at least one valid baseline sample between screening to dose administration on day 1. Subjects without a valid baseline sample will be excluded from PD assessments where the derived metric is baseline adjusted.
- The PK population will include all subjects who receive study drug and have at least 1 estimable PK parameter after dosing. Subjects with all samples below the lower limit of quantification will not be included in PK population summaries.
- The PK/PD population (exposure-response population) will include all subjects from the PK and PD populations, including subjects treated with placebo or subjects

- where all PK samples were below the lower limit of quantification. The PK/PD population will be used for the model-based exposure-response analysis.
- Subjects who discontinued from the study before their assigned end of study day (referred to as early termination subjects) will be excluded from pharmacokinetic and pharmacodynamic parameter summary calculations.
- The safety population will include all subjects who receive at least 1 dose of any of the study drugs.

6. Data Screening and Acceptance

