5.6.4 Discharge (or Early Termination)

The following procedures and assessments will be performed before the subject is discharged from the study (Day 63 or Day 123) or at early termination according to Table 9-1:

- Perform a serum pregnancy test (female subjects only)
- Record concomitant medications
- Monitor for AEs
- Perform clinical laboratory tests (hematology, serum chemistry, and urinalysis)
- Measure vital signs (blood pressure, heart rate, respiratory rate, and oral body temperature)
- Perform a safety 12-lead ECG
- Perform a complete physical examination
- Measure height, weight, and calculate body mass index
- Perform alcohol and drug screening (amphetamines, barbiturates, benzodiazepines, cannabinoids, cocaine, alcohol, opiates, phencyclidine, propoxyphene, and methadone)
- Collect a single PK blood sample (5 mL)
- Collect whole blood eosinophil blood sample (3.5 mL) for flow cytometry
- Collect whole blood (5 mL) and process for plasma for proteomic and small RNA transcriptomic analyses
- Collect urine (3-5 mL) for omic analysis (e.g., transcriptomics and/or metabolomics)
- Remove IV catheter (if applicable)
- Discharge subject from the study clinic after completion of all study procedures

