3.2. Sample size

Approximately 86 healthy subjects will be enrolled (72 subjects for treatment and up to 14 potential replacement subjects). Subjects will be randomized to one of 8 different active treatment arms (i.e. 8 per treatment arm) or placebo. This study did not have any formal sample size or power calculations. Doses expected to characterize the dynamic range of the primary PD parameter (eosinophils) were selected. A total of 8 subjects are planned per dose as a typical sample size for estimating values and variability of PK and PD measures in single ascending dose trials.

4. Study Endpoints

4.1. **Primary Endpoints**

- Peripheral blood eosinophil area under the effect curve from time zero to last onstudy timepoint (AUEC_{0-t}, referred to as AUEC for brevity).
- Maximum decrease from baseline in eosinophils (ΔEosinophil_{dec. max})

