7.5. PK/PD Analyses

The dose- and exposure-response relationship between baseline-adjusted AUEC for eosinophils and $\Delta Eosinophil_{dec, max}$ and mepolizumab and reslizumab will be explored graphically (separate assessments for both response measures). Based on these observations, model-based analyses using statistical software will be conducted separately for each drug with respect to each of the above-mentioned PD measures.

The model-based analysis will explore both dose and exposure (i.e., AUC_{0-inf}, referred to as AUC below) as the dependent variable. All dose levels for a drug, as well as placebo data, will be combined for the analysis. Model selection will be based on the initial graphical assessment and will be selected from one of the following structures – linear,

E_{max}, and sigmoidal E_{max}. Multiple models may be evaluated based on the initial graphical analysis, in which case model selection will be based on a combination of goodness of fit plots, parameter uncertainty (i.e., parameter confidence intervals including zero), and Akaike's information criterion (AIC). General representations for each of the model structures and parameterizations is shown below:

Dose-relationship

Linear: Response $\sim E_0 + \text{Slope * Dose}$

 E_{max} : Response ~ $E_0 + E_{\text{max,dose}} * Dose / (Dose + ED_{50})$

Sigmoidal E_{max} : Response $\sim E_0 + E_{max,dose} * Dose^{\gamma} / (Dose^{\gamma} + ED_{50}^{\gamma})$

Exposure-relationship

Linear: Response $\sim E_0 + \text{Slope * AUC}$

 E_{max} : Response ~ E_0 + $E_{\text{max,exp}}$ * AUC / (AUC + EC_{50})

Sigmoidal E_{max} : Response $\sim E_0 + E_{max,exp} * AUC^{\gamma} / (AUC^{\gamma} + EC_{50}^{\gamma})$

Model evaluation will include residual variability error term but will not include any random effects or covariate evaluation on fixed effect.

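### SAP 5 drops early leavers from every PK and PD summary, even Cmax and Tmax already observed, yet by its wording leaves their AUEC0-t, cut at exit, in the SAP 7.5 models

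*SAP*

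**What the plan says.** **Summaries.** SAP 5 has one rule for early leavers: "Subjects who discontinued from the study before their assigned end of study day (referred to as early termination subjects) will be excluded from pharmacokinetic". The sentence goes on to cover pharmacodynamic parameters, and what it excludes subjects from is the parameter summaries. No parameter is excepted. SAP 4.2 and 4.3 list Cmax and Tmax among the PK parameters. SAP 7 keeps excluded data in the listings.

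**Models.** Entry to the PK and PD populations needs dosing and one estimable parameter, not completion. SAP 5 then says: "The PK/PD population (exposure-response population) will include all subjects from the PK and PD populations". It adds: "The PK/PD population will be used for the model-based exposure-response analysis". In SAP 7.5, "The model-based analysis will explore both dose and exposure", with AUC0-inf as the exposure measure, and "Model evaluation will include residual variability error term but will not include any random effects or covariate evaluation on fixed effect".

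**The AUEC of an early leaver.** SAP 4.1 defines the endpoint as "area under the effect curve from time zero to last onstudy timepoint". SAP 7.3.1 computes it from all on-treatment timepoints, and SAP 6.1 does not impute missed samples. Under Protocol 5.6.4 the exit procedures "will be performed before the subject is discharged from the study (Day 63 or Day 123) or at early termination", and one of them is: "Collect whole blood eosinophil blood sample (3.5 mL) for flow cytometry".

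**Context.** Assigned follow-up ends on Day 63 in groups A, B, E and F, and on Day 123 in the others (SAP 3.1). Protocol 5.5.2 allows up to 14 replacements, each on the treatment of the subject replaced.

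**The concern.** The two halves of the rule pull in opposite directions.

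In the summaries, a group D subject who leaves between Day 93 and Day 123 loses a Cmax that may have been settled weeks earlier. That parameter does not need sampling to the assigned end day.

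In the models, the same subject's AUEC0-t, the parameter that does depend on length of follow-up, stays in and is treated like a completer's. Nothing in SAP 7.5 marks it as shorter. A replacement adds a subject but does not take the cut value out of the fit.

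The exposure-response parameters are a secondary endpoint (SAP 4.2), and the study exists to inform the design of later similarity studies. With 8 subjects per arm, one distorted value can carry weight. Summaries and models would also rest on different sets of subjects without the SAP saying so.

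**Working it through.** **Plan figures.** 9 groups x 8 = 72, and 72 + 14 = 86, as stated. SAP 3.2 says there was no formal sample size or power calculation, so there is no other stated figure to reproduce. If all 14 replacements were used for early leavers, up to 86 subjects could feed the models against 72 in the summaries.

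**1. Cost in the summaries.** The upper 95% limit for an SD, as a multiple of its estimate, is sqrt(df / chi2(0.025, df)) with df = n - 1.

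| n | 7 | 8 | 9 |
|---|---|---|---|
| multiple | 2.20 | 2.04 | 1.92 |

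Keeping one leaver's Cmax moves the limit from 2.04 to 1.92 if the leaver was replaced (8 to 9 values), and from 2.20 to 2.04 if not (7 to 8).

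**2. How much of the AUEC is cut (assumed profile).** The documents give no effect profile. Assume the effect rises linearly from Day 1 to a nadir on Day N and falls linearly to zero on Day R. For exit on Day x between N and R, the captured share is 1 - (R - x)^2 / ((R - N)(R - 1)). For N = 7, R = 63, x = 21 this is 1 - 42^2 / (56 x 62) = 0.49.

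| Exit day | N7/R63 | N7/R93 | N14/R63 | N14/R93 |
|---|---|---|---|---|
| 21 | 0.49 | 0.34 | 0.42 | 0.29 |
| 28 | 0.65 | 0.47 | 0.60 | 0.42 |
| 42 | 0.87 | 0.67 | 0.85 | 0.64 |
| 63 | 1.00 | 0.89 | 1.00 | 0.88 |

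Once recovery has come before exit, nothing is lost from an undivided area.

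**3. Effect on the dose model (assumed inputs).** I fitted E0 + Emax x Dose / (Dose + ED50) by noise-free least squares to doses 0, 3, 6, 12 and 24 mg. There were 8 completers per dose plus one replaced leaver whose response is f times the true value, with f = 0.3 to 0.7 and true ED50 3 to 24 mg.

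| Leaver in group | Shift in Emax | Shift in ED50 |
|---|---|---|
| A (3 mg) | +1% to +3% | +1% to +16% |
| B (6 mg) | +0.3% to +7.5% | +5% to +15% |
| C (12 mg) | -4% to +10% | -5% to +25% |
| D (24 mg) | -3% to -19% | -9% to -27% |

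A leaver at the top dose lowers the plateau. A leaver at 3 or 6 mg steepens the apparent climb, so both parameters rise. In group C the sign depends on the true ED50. For group D with f = 0.9 the shifts are only -1.1% to -3.3% (Emax) and -3.1% to -4.6% (ED50). The group D shifts at f = 0.3 to 0.7 equal 0.11 to 1.27 standard errors of the fit, at n = 40 and an assumed residual SD of 10-20% of Emax. Reslizumab doses have the same 1:2:4:8 spacing, so the same shifts hold for ED50 0.1 to 0.8 mg/kg.

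**4. Effect of the metric.** SAP 7.3.1 names pAUEC for the primary analysis and gives no formula. If pAUEC divides by baseline times elapsed time (an assumption), the ratio of a leaver's value to the full Day 123 value is the captured share x 122 / (x - 1). For exit on Day 21 with N7/R63 it is 0.49 x 122 / 20 = 3.0; with N14/R93 it is 0.29 x 122 / 20, about 1.75. Across exits on Days 21 to 42 the ratio is 1.75 to 3.0, so the response is overstated.

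**The case against.** **The SAP never says that early leavers stay in the models.** The exclusion sits under the same heading as the population definitions and might be meant to apply wherever a parameter is used. This stands as ambiguity. The wording nevertheless limits the rule to summaries. SAP 5 also treats subjects with all samples below quantification in that way, out of PK summaries and in the PK/PD population.

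**SAP 5 assigns the PK/PD population to the exposure-response analysis only.** Correct. Its use for the dose models is inferred from SAP 7.5, which treats dose and exposure as one model-based analysis.

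**The exposure models are partly protected.** Correct. SAP 7.4 admits AUC0-inf only with at least 3 terminal concentrations and adjusted R2 above 0.80, so some leavers drop out. The dose models have no such filter.

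**A completer set with same-treatment replacements gives one common set for all parameters.** This is a real advantage, and it is why the summary half is minor.

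**The protocol ends AUEC at return to baseline** (5.7.2.3.1, with dose-specific intervals in 5.9.6.1). Under that definition, exit after recovery cuts nothing. But SAP 4.1 runs to the last on-study timepoint, and exit before recovery cuts the area under either definition. The unequal Day 63 and Day 123 horizons among completers are a separate matter.

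**Stronger reading.** A reader might infer that a cut AUEC always understates the response and biases Emax and ED50 downward. The documents do not support that. The sign reverses in groups A and B, varies in C, and turns on an unstated pAUEC formula.

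**Conclusion.** The point holds on the wording of the SAP, as something to consider, with medium confidence.

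- **Summaries:** usable Cmax and Tmax values are discarded. The loss is modest and recoverable. It would be wrong to infer that it threatens the study.
- **Models:** followed as written, the SAP fits an AUEC0-t that stops at exit as if follow-up were complete. No other section corrects this. The case is clearest for the dose models, subject to the inference about which population they use.
- **Size and direction:** size unknown, because the documents give neither a dropout rate nor an effect profile. Direction depends on the arm of the leaver and on whether the area is divided by elapsed time. All percentages above are illustrations that rest on one leaver, the assumed capture and ED50 ranges, and an Emax model.

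Keeping AUEC0-t summaries to completers is sound. The gap is that the models do not follow the same rule.

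**What to change.** 1. In SAP 5, make the exclusion parameter-specific. Summarise Cmax and Tmax for every dosed subject whose sampling covers the observed peak and its decline, for example those sampled through the in-house period. The documents give no Tmax for either drug, so the condition should be the covered peak, not a fixed day alone. Report n per parameter and arm.
2. Keep AUEC0-t summaries to subjects who reach their assigned end of study day. State in SAP 5 and 7.5 that an AUEC0-t or pAUEC truncated by early termination is also left out of the primary dose- and exposure-response models, with one sensitivity fit that includes it. Name the population for the dose models in the same sentence.

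I propose no change to the summary rule for maximum decrease, which searches all on-treatment timepoints, or to the SAP 7.4 criteria for AUC0-inf.

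**Cost:** a few sentences, an inclusion flag per parameter and one extra fit. No new data are needed and the primary endpoint is unchanged. The downside is that n will differ between parameters, so there is no longer a single common completer set.

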6.1. Handling of Missing and Incomplete Data

The following imputation of missing values will be done:

- Pharmacokinetic measurements below the quantification limits will be considered equal to zero for all analyses.
- Non-pharmacokinetic measurements (e.g., eosinophils) below the quantification limits will be considered equal to the lower limit of quantification for all analyses unless explicitly noted otherwise.
- Missing pharmacokinetic or pharmacodynamic data (e.g., skipped outpatient visit) will not be imputed.
- For baseline adjusted measures, samples from Day 1, time 0 will be used for calculating this derived metric. In cases where the Day 1, time 0 sample is missing or invalid, the sample collected at check-in (Day -1) will be used, followed by the screening sample. If none of these samples are available or valid, then no baseline value will be calculated for the subject.

7. General Statistical Considerations

All data will be presented in data listings. Data from subjects excluded from an analysis population will be presented in the data listings, but not included in the calculation of summary statistics. In addition, the reason for exclusion from an analysis population will be noted for individual subjects.

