5.7.1.3 Pharmacokinetic Parameters

The following PK parameters will be determined for each subject:

- Maximum concentration (observed peak drug concentration) (C_{max})
- Time at which C_{max} occurs (T_{max})
- AUC from time 0 to the sampling time corresponding to the last quantifiable concentration (C_{last}) (AUC_{0-t})
- Elimination rate constant (K_{el})
- Terminal half-life ($t_{1/2}$)

- AUC from time 0 extrapolated to infinity (AUC_{0-inf})

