	2.3.	Exploratory Objective	7
3.	Stuc	ly Overview	8
	3.1.	Study design	8
	3.2.	Sample size	9
4.	Stuc	ly Endpoints	9
	4.1.	Primary Endpoints	9
	4.2.	Secondary Endpoints	10
	4.3.	Exploratory Endpoints	10
5.	Ana	lysis Populations	10
6.	Data	Screening and Acceptance	11
	6.1.	Handling of Missing and Incomplete Data	11
7.	Gen	eral Statistical Considerations	11
	7.1.	Subject Disposition	12
	7.2.	Demographics and Baseline Characteristics	12
	7.3.	Pharmacodynamic Analyses	12
	7.3.	Peripheral Blood Eosinophils	12
	7.4.	Pharmacokinetic Analyses	13
	7.5.	PK/PD Analyses	13
	7.6.	Exploratory Omics Analysis.	14
	7.7.	Safety Analyses	14
	7.7.	Adverse Events	14
	7.7.2	2 Clinical Laboratory Tests	15
	7.7.3	Wital Sign Measurements	15
	7.7.4	Safety 12-lead Electrocardiograms	15
	7.7.	5 Physical Examinations	15

	7.7.6	Other Safety Data	15
8.	Data Qua	ality Assurance	15
Atta	chment A	. Pharmacokinetic, Pharmacodynamic, and Biomarker Sample Collection Sch	edule
			17
Atta	chment B	Randomization Schedule	18

Table of Abbreviation

Abbreviation	Definition
$\mathrm{AUC}_{0 ext{-}\mathrm{inf}}$	area under the concentration-time curve from time zero to infinity
$\mathrm{AUC}_{0\text{-t}}$	area under the concentration-time curve from time zero to last on-study sample
$\mathrm{AUEC}_{0 ext{-t}}$	area under the effect curve from time zero to last on-study sample
AUEC	area under the effect curve
$pAUEC_{0-t}$	percentage area under the effect curve from time zero to last on-study sample
CL/F	apparent clearance
C_{max}	maximum observed concentration
EC ₅₀	the exposure that gives-half maximal response, model parameter
ED_{50}	the dose that gives-half maximal response, model parameter
E _{max,exp}	maximum PD response, model parameter – concentration analysis
$E_{\text{max,dose}}$	maximum PD response, model parameter - dose analysis
$\Delta Eosinophil_{dec, max}$	maximum decrease from baseline in eosinophils
FDA	Food and Drug Administration
K_{el}	elimination rate
mg	milligram
PD	pharmacodynamic
PK	pharmacokinetic
RNA	ribonucleic acid
SC	subcutaneously
SD	standard deviation
T_{max}	time of maximum concentration (C_{max})
$t_{1/2}$	terminal half-life
V/F	apparent volume of distribution

Change Log

Version	Section	Changes
2	5	Added that 'Subjects who did not complete their treatment (referred to as early termination subjects) will not be included in PK and PD parameter summary calculations.'

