7.4. Pharmacokinetic Analyses

Individual serum concentration versus time plots for mepolizumab and reslizumab groups will be presented for each participant. AUC_{0-inf} and C_{max} will be calculated for each participant using all on treatment timepoints as part of the secondary analysis. In addition, the following PK parameters will be calculated for each individual as exploratory analyses: AUC_{0-t}, T_{max}, apparent clearance (CL/F), apparent volume of distribution (V/F), elimination rate (K_{el}), and terminal half-life (t_{1/2}) PK parameters will be calculated for each participant using all on treatment timepoints. All parameters will be summarized using descriptive statistics (n, geometric mean, coefficient of variation, minimum, median, interquartile range, and maximum) for each mepolizumab and reslizumab treatment arm.

Calculations will be performed using non-compartmental analysis packages available in a statistical software. Serum concentrations below the limits of quantification will be set to zero for the purpose of this analysis. Subjects with all samples below the limit of quantification will be excluded from PK summaries. AUC_{0-inf} , $t_{1/2}$, and K_{el} for subjects will only be included for subjects with 3 or more concentration values on the terminal portion of the pharmacokinetic curve and with an adjusted coefficient of determinations (R^2) greater than 0.80.

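### The SAP runs AUC0-t to the end of study with values below quantification set to zero, so it is not the Protocol's AUC0-t and depends on the visit calendar

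*SAP*

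**What the plan says.** On values below quantification, SAP 6.1 reads: "Pharmacokinetic measurements below the quantification limits will be considered equal to zero for all analyses". SAP 7.4 repeats it for the non-compartmental analysis: "Serum concentrations below the limits of quantification will be set to zero for the purpose of this analysis". Neither distinguishes samples before the first measurable value, between measurable values, or after the last one. The companion bullet in SAP 6.1 for non-PK measurements allows stated exceptions; the PK bullet does not. The Protocol has no rule for values below quantification.

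On AUC0-t there are three wordings:

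- Protocol 5.7.1.3 (and the synopsis): "AUC from time 0 to the sampling time corresponding to the last quantifiable concentration".
- SAP 4.3: "area under the curve from time 0 to end of study".
- SAP abbreviation table: "area under the concentration-time curve from time zero to last on-study sample".

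The SAP change log does not mention the difference. SAP 4.2 makes AUC0-inf and Cmax the PK secondary endpoints, SAP 4.3 lists AUC0-t as exploratory, and SAP 7.5 uses AUC0-inf as the exposure measure in the models. The SAP gives no formula for AUC0-inf, does not define Clast, and names neither a trapezoid rule nor an analysis program.

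**The concern.** One symbol stands for two quantities. Under the Protocol, AUC0-t ends where measurement ends. Under the SAP it continues to the final visit, with zeros in place of every later unmeasurable sample. The trapezoid rule then joins the last measurable concentration to a zero at the next visit. The area of that join depends on how long the subject waited for the next visit, which is a feature of the schedule and not of the drug.

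The study is meant to report values and variability of PK measures for planning later similarity studies. An AUC0-t with a calendar-dependent component is not comparable with one computed in the Protocol's way, nor between arms followed to Day 63 and arms followed to Day 123. There is also a loose end for AUC0-inf: an unqualified zero rule leaves it open whether a trailing zero could be taken as the concentration from which the tail is extrapolated.

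**Working it through.** The plan gives no figure to reproduce. The check compares the definitions and then sizes the difference.

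**Inputs from the documents**

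- Sampling (Protocol 5.7.1.1, SAP Attachment A): daily to Day 14, weekly to Day 63, then Days 93 and 123. The gaps are 1, 7 and 30 days.
- Follow-up (SAP 3.1): Groups A, B, E and F to Day 63; Groups C, D, G, H and I to Day 123.
- Dosing on Day 1, so Day 63 is 62 days after dosing.

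**Assumptions, not in the documents:** quantification limit (LLOQ), half-life, assay CV, and a linear trapezoid. The worked profile is IV, one-compartment, treated as a bolus, with Cmax = 1 and a half-life of 20 days, so the rate constant is ln 2/20 = 0.03466 per day.

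**Step 1. Added area.** Between Clast and the first trailing zero, the area is (Clast + 0)/2 x gap.

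- 7-day gap: 7/2 = 3.5 x Clast.
- 30-day gap: 30/2 = 15 x Clast.
- Later zeros add (0 + 0)/2 x gap = 0.

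**Step 2. One curve, two arms.** Take the LLOQ as 5% of Cmax. The concentration is exp(-0.03466 x 62) = 0.1166 on Day 63 (measurable) and exp(-0.03466 x 92) = 0.0412 on Day 93 (below the limit). The trapezoid area to Day 63 on the study's sampling days is 25.56.

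| | Protocol AUC0-t | SAP AUC0-t | Difference |
|---|---|---|---|
| Followed to Day 63 | 25.56 | 25.56 | 0% |
| Followed to Day 123 | 25.56 | 25.56 + 15 x 0.1166 = 27.31 | +6.8% |

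The concentrations to Day 63 and the assay are identical; only the visit schedule differs.

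**Step 3. A weekly gap.** Take the LLOQ as 20% of Cmax. Day 42 (41 days) gives 0.2415, measurable; Day 49 (48 days) gives 0.1895, below the limit. The Protocol area is 21.94. The SAP area is 21.94 + 3.5 x 0.2415 = 22.79, which is +3.9%.

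**Step 4. Range for AUC0-t.** Noise-free SC and IV profiles with half-lives of 10, 20 and 30 days and an LLOQ of 1, 5, 10 and 20% of Cmax gave differences of 0% to 12.1%. The zeros are the cases with no trailing sample below the limit. Simulated profiles with a half-life of 15-30 days, assay CV of 10-20% and the limit crossed during sparse sampling gave a median of about 3-7% and a 10th-90th percentile range of about 1-15%.

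**Step 5. AUC0-inf and trailing zeros.** For the Step 2 profile in a Day-123 arm:

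- Extrapolated from the last positive value: 25.56 + 0.1166/0.03466 = 25.56 + 3.37 = 28.93. The trailing zeros play no part.
- If the final zero were taken as Clast: 27.31 + 0 = 27.31, which is -5.6%. Over the Step 4 noise-free grid this reading changes AUC0-inf by -21.2% to +0.1%.

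The SAP does not say which of the two applies.

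**The case against.** AUC0-t is exploratory in the SAP, the primary endpoints are eosinophil measures that this rule does not touch, and there is no hypothesis test on PK. All data are listed, so either area can be recomputed. An analysis program may also ignore trailing zeros. All of this is fair and keeps the point minor, but none of it removes the conflict between the two definitions.

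A reader might infer something stronger: that the zero rule also cuts the secondary endpoint, because a value below the limit between two measurable samples carves a notch out of the curve. By linear trapezoid such a zero does remove C x (gap before + gap after)/2. The material does not support making this the main point:

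- Under assumed half-lives and LLOQ, such values were uncommon (about 0-11% of subjects who cross the limit, although other assumptions reached 32%) and lowered those subjects' AUC0-inf by about 5-6%.
- The arm geometric mean moved by about 2% at most, mostly under 0.5%. A separate set of assumptions, with the SAP 7.4 acceptance rule applied, gave 0-3.3% (under 1% in 26 of 30 settings) and at most 0.5 percentage points on the geometric CV.
- Treating these values as missing did not bring AUC0-inf nearer the truth. In that second set, the affected subjects' median ratio to the true value was 0.99-1.13 with zero and 1.04-1.24 with missing. This is partly offsetting error, since a later sample that is high by noise inflates the tail, and it does not justify zero in principle.

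Two further inferences also fail. That the error falls mainly in the low-dose arms cannot be shown without an LLOQ, and the 30-day gap occurs only in the Day-123 arms. That analysis software would leave the problem uncorrected cannot be shown either, since SAP 7.4 names no program or setting.

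**Conclusion.** The point holds as a mismatch of definitions with a small numerical consequence. As written, the SAP's AUC0-t is not the Protocol's, and the excess is set by the interval to the next visit. The size, a median of about 3-7% higher, rests on the assumed half-life of 15-30 days and an LLOQ crossed in the weekly or monthly phase. If no trailing sample is below the limit, the two definitions give the same number.

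For AUC0-inf the finding is only an open definition: trailing zeros have no effect when the tail starts from the last positive value, and the SAP should say that it does. The documents do not support a claim that the secondary endpoint is materially biased. This is a low-priority correction, worth making because it costs almost nothing and changes a reported number.

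**What to change.** - SAP 4.3 and the abbreviation table: define AUC0-t to the last quantifiable concentration, as in Protocol 5.7.1.3. If the area to the end of study is wanted as well, give it a different name.
- SAP 6.1 and 7.4: apply zero only to samples before the first quantifiable one, and drop values after the last quantifiable sample.
- SAP 7.4: define Clast as the last quantifiable concentration and state that AUC0-inf is extrapolated from it.
- Keep zero exposure for placebo subjects and for subjects with every sample below the limit in the PK/PD population (SAP 5).
- Optional: treat values below the limit between two quantifiable samples as missing. This is a conventional clean-up of the observed area, with no shown gain in the accuracy of AUC0-inf and a negligible effect on arm summaries.

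The cost is a few lines of SAP text and an analysis setting. No new data are needed.
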